3.2.10 Organ Function Requirements

- Hepatic function: Patients must have adequate liver function, defined as
 - Total bilirubin <2.0x the upper limit of normal and
 - Direct bilirubin within normal limits and
 - SGPT (ALT) <2.5 x the upper limit of normal.
 - Patients with Gilbert syndrome are excluded from the requirement of a normal bilirubin but they must have an indirect bilirubin of <6mg/dl, and a direct bilirubin of <0.5mg/dl in order to be eligible. (Gilbert syndrome is found in 3-10% of the general population and is characterized by mild, chronic hyperbilirubinemia in the absence of liver disease or overt hemolysis).
- Hematological function: Patients must have adequate bone marrow function defined as:
 - peripheral absolute granulocyte count of >1000/mm³,
 - hemoglobin >8 gm/dL, Patients may be transfused with RBC's
 - platelet count >100,000/mm³. Independent of transfusion.
- Renal function: Patients must have an age-adjusted normal serum creatinine (see below) OR a creatinine clearance or GFR >/= or more than 60 mL/min/1.73 m².

Age (years)	Maximum Serum Creatinine (mg/dl)
<5	0.8
5<age<10	1.0
10<age<15	1.2
>15	1.5

- Adequate Pulmonary function defined as:
 - no evidence of dyspnea at rest and pulse oxymetry >94% .

3.2.11 If history of depression or psychiatric illness, has to be well controlled with antidepressants and/or under psychiatrist/ psychologist care.

3.3 EXCLUSION CRITERIA

3.3.1

Patients who are receiving concurrent chemotherapy, or who are currently receiving other investigational chemotherapeutic agents or concurrently receiving radiation.

3.3.2

Patients with a known hypersensitivity to interferon-alpha.

3.3.3

Prior use of Pegylated interferon or interferon.

3.3.4

Less than 2 years since completion of radiation therapy.

3.3.5

Pregnant or breast-feeding females are excluded because the effects of pegylated interferon alfa-2b on the unborn fetus are unknown

3.3.6

Patients with clinically significant unrelated systemic illness (including autoimmune disease, serious infections or significant cardiac, pulmonary, hepatic or other organ dysfunction) which in the judgment of the Principal or Associate Investigators would compromise the patient's ability to tolerate this therapy or are likely to interfere with the study procedures or results.

3.3.7

Dental braces or prosthesis that interferes with MR imaging.

3.3.8

History of noncompliance to medical regimens.

3.3.9

Patients unwilling to or unable to comply with the protocol.

3.3.10

Patients with a positive history of Hepatitis B or Hepatitis C.

3.3.11

Male patient whose sexual partner(s) are women of childbearing potential who are not willing to use adequate contraception, during the study and for 8 weeks after the end of treatment.

3.3.12

Patients should not receive immunization with attenuated live vaccines within one week of study entry or during study period. Close contact with those who have received attenuated live vaccines should be avoided during treatment with pegylated interferon. Examples of live vaccines include intranasal influenza, measles, mumps, rubella, oral polio, BCG, yellow fever, varicella and TY21a typhoid vaccines.

3.3.13

Patient with diagnosis of Diffuse Intrinsic Pontine Glioma.

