3.2 Eligibility Criteria

All clinical and laboratory studies to determine eligibility must be performed within **14 days** prior to enrollment, except MRI brain and/or spine within **30 days** prior to enrollment. If more than 14 calendar days elapse between the date eligibility studies were obtained and the start date of treatment, then the following studies must be repeated prior to treatment: CBC with differential, bilirubin, ALT (SGPT) and serum creatinine. If any of these repeat laboratory studies are outside the parameters required for eligibility (labs may again be repeated within 48-72 hours), then the patient is off protocol therapy. Imaging studies are required within **30 days** prior to enrollment.

Important note: The eligibility criteria listed below are interpreted literally and cannot be waived. All clinical and laboratory data required for determining eligibility of a patient enrolled on this trial must be available in the patient's medical or research record which will serve as the source document for verification at the time of audit.

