3.2 INCLUSION CRITERIA

3.2.1 Age

Patients must be older than 3 years and less than or equal to 25 years of age at the time of enrollment

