3.4 Regulatory

3.4.1

All patients and/or their parents or legal guardians must sign a written informed consent.

The investigational nature and research objectives of this trial, the procedures and treatments involved and their attendant risks and discomforts and benefits, and potential alternative therapies will be carefully explained to the patient, the patient's parents or guardian if he/she is a child, or previously assigned DPA and a signed informed consent document will be obtained prior to entry onto the study.

The PI or an associate investigator on the trial will obtain consent. Where deemed appropriate by the clinician and the child's parents or guardian, the child will also be included in all discussions about the trial and verbal assent will be obtained. The parent or guardian will sign the designated line on the informed consent attesting to the fact that the child has given assent.

3.4.2

All institutional, FDA, and NCI requirements for human studies must be met.

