Criteria to start a cycle: ANC ≥ 1,000/μL and platelet count ≥ 100,000/μL (transfusion independent). This cycle lasts 28 days.

DRUG	ROUTE	DOSAGE	DAYS	IMPORTANT NOTES	OBSERVATIONS
Pegylated interferon	SQ	1 mcg/kg/dose Max dose is 150 mcg/dose	weekly (+/-5 days)	Premed with Tylenol or ibuprofen as needed.	a. CBC with differential b. CMP, Magnesium, Phosphorous, Calcium, Uric Acid. c. PT/PTT d. Urinalysis e. Performance Score f. Hx, PE, Neuro Exam, Wt, Ht, VS. g. pregnancy test h. Assessment of clinical toxicity/ adverse events i. QOL questionnaire j. MRI of brain and/or spine k. Am Cortisol, Free T4, TSH. l. Ophthalmology Evaluation m. Pegylated interferon Diary n. lumbar puncture (See section 7.1) OBTAIN OTHER STUDIES AS REQUIRED FOR GOOD PATIENT CARE

Cycle- 28 Days (+/- 5)	Date Due	Date Given	Chemotherapy Dose	Studies
1				a-i, k, l, o
				a, b, e, f, h, m
2				a, b, e, f, h, m

Cycle- 28	Date Due	Date Given	Chemotherapy Dose	Studies
3				a, b, e, f, h, m
4				a, b, d, e, f, h, i, j, m, n
5				a, b, e, f, h, m
6				a, b, e, f, h, l, k, m
7				a, b, d, e, f, h-j, m, n
8				a, b, e, f, h, m
9				a, b, d, e, f, h, m
10				a, b, d, e, f, h-j, m, n
11				a, b, e, f, h, m
12				a, b, e, f, h, k, l, m

Cycle- 28				
Cycle- 28 Days (+/- 5)	Date Due	Date Given	Chemotherapy Dose	Studies
13				a, b, d, e, f, i, j, m, n
14				a, b, e, f, h, m
15				a, b, d, e, f, h, m
16				a, b, d, e, f, h-j, m, n
17				a, b, e, f, h, m
18				a, b, e, f, h, l, k, m
19				a, b, d, e, f, h-j, m, n
20				a, b, e, f, h, m
21				a, b, d, e, f, h, m
22				a, b, d, e, f, h-j, m, n

Cycle- 28	Date Due	Date Given	Chemotherapy Dose	Studies
23				a, b, e, f, h, m
24				a, b, d, e, f, h, i, k, l, m
25				a, b, d e, f, h- j, m, n
26				a, b, e, f, h, m
END of therapy				

a- Obtain weekly. If patient develops grade 4 neutropenia, CBCs should be checked **every 3 to 4 days** until recovery to grade 3.

n-Obtain prior to starting cycle one only for females of childbearing potential. For the rest of the protocol follow institutional policies about pregnancy testing.

j-Obtain after every third cycle and as clinically indicated. MRI of spine obtain at same time points as brain MRI, for patients with known or suspected spinal disease.

See Section 5.0 for Dose Modifications for Toxicities

For supportive care guidelines see:

http://members.childrensoncologygroup.org/prot/reference_material.asp

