7.1 Required Clinical, laboratory and Disease Evaluations

All baseline studies must be performed within **14 days** prior to enrollment and MRI of brain and/or spine within **30 days** prior to enrollment. **Obtain other studies prior to start of subsequent cycles and as otherwise indicated.**

STUDIES TO BE OBTAINED	Pre-study ¹ (Baseline)	Prior to Each Cycle	Q2 weeks Cycle 1	Prior to cycle 4,7,10,13 16,19,22,25	Every six months	When patient is removed from protocol Therapy**
History	X	X	X			X
Physical Exam with neurological exam (Wt, Ht and VS)	X	X	X			X
Performance Status	X	X				X
CBC, platelets and differential	X	X	X ⁵			X
CMP, magnesium phosphorous, calcium, Uric acid	X	X	X ⁵			X
PT, PTT	X					
AM cortisol, Free T4, TSH, (growth hormone if clinically indicated)	X				X	X
Urinalysis / urine dipstick	X			X		X
Urine or serum pregnancy test	X ²					
MRI of brain w/wo contrast	X ³			X		X
MRI spine	X ⁴			X ⁶		X
LP for CSF cytology	X ⁹			X ¹⁰		
Ophthalmology Evaluation ⁷	X				X	X
QOL questionnaire ⁸	X			X		X
Pegylated interferon Diary		X	X			X
Assessment of clinical toxicity/adverse events						X

1-Must be performed within 14 days prior to receiving the study drug with the exception of MRI of brain and spine. MRI of the brain and or spine can be done in within **30 days** prior to enrollment.

2-Required for all females of childbearing potential as a baseline study, then continue to follow institutional guidelines regarding pregnancy testing.

3- With and without contrast; within **30 days** prior to enrollment.

4-For patients with a known history of spinal disease, within **30 days** prior to enrollment on the study or when it is clinically indicated by the treating physician.

5-If no > Grade I toxicity during the previous cycle, then every month in subsequent cycles through cycle 27.

6-For patients with history of spinal disease; obtained at the same time points as MRI brain until no evidence of disease on 2 consecutive spine MRIs. Also when patient is removed from protocol therapy.

7-Ophthalmology evaluation only needed for patients with optic pathway gliomas. (Sooner than interval designated if indicated by neuro-ophthalmologist/ophthalmologist)

8- Children younger than 7 years and older will complete the parent survey only. For any child older than 7 years will complete also the patient questionnaire for Quality of life. QOL questionnaires are only available for English speaking patients. They have not been validated in other languages.

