-PT and PTT will be obtained at a baseline. Obtain later on only if clinically indicated.

-Endocrine Function Tests: First morning cortisol, free T4, TSH every six months or sooner if clinically indicated. Growth hormone testing to be done if clinically indicated.

-Urinalysis or urine dipstick is acceptable. Urinalysis will be obtained if urine dipstick is abnormal. If urine evaluation is normal, then check at the same time points as the brain MRI.

-Urine Pregnancy Test or Serum Pregnancy Test: required for females of childbearing potential. Additional pregnancy test per institutional guidelines. At Aflac, monthly pregnancy test for females of childbearing potential.

Radiology:

MRI of the brain/and or spine will be performed every 3 cycles throughout the duration of the treatment. Initial evaluation will be performed at the end of the cycle #3. Patients with a history of spinal disease will undergo a spine MRI at the same time points until there is no evidence of disease on 2 consecutive spine MRI's. All brain MRIs will include, if possible, diffusion-weighted, dynamic-enhanced, dynamic susceptibility, DT-MRI, and other MR sequences in addition to the standard MR sequences. All MRI's will be reviewed and interpreted with the neuroradiologist.

Quality Of Life Questionnaire:

- We have chosen the Peds-**FACT-Br**: Pediatric - For patients with Brain cancer, ages 7 to 12 year old or greater than 12 years. Additionally, we will include the parent QOL questionnaire. There are 2 versions, for patients younger than 12 years and for patients 12 years or older. To be administered prior to start therapy and q3 months at the same interval as MRIs. See appendix 2A, 2B, 2C and 2D.
- QOL questionnaires are not available for non -English speaking patients and they have not been validated in other languages. QOL questionnaires are not required for non-english speaking patients

Post-Therapy Evaluation

The following tests and procedures should be performed, if possible, at the time a patient comes off therapy, regardless of the reason for coming off therapy, unless the test or procedure has been performed in the past 14 days.

- History and physical examination.
- Performance status.
- Assessment of clinical toxicity/adverse events.
- Laboratory Assessment:
 - Complete blood count, differential and platelet count
 - SGPT (ALT), bilirubin (total and direct), BUN, creatinine, electrolytes, calcium,
 - Magnesium, phosphorus, uric acid.
 - Urinalysis

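### The eligibility criteria address contraception only in relation to male patients; none asks it of female patients of childbearing potential

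*Combined protocol and SAP*

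**What the plan says.** All places are in the combined protocol and SAP.

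- **3.3.11** excludes a "Male patient whose sexual partner(s) are women of childbearing potential who are not willing to use adequate contraception, during the study"; its reach extends 8 weeks past treatment.
- **3.3.5** is the only criterion specific to females: "Pregnant or breast-feeding females are excluded because the effects of pegylated interferon alfa-2b on the unborn fetus are unknown".
- **3.2, important note**, on how the criteria are applied: "The eligibility criteria listed below are interpreted literally and cannot be waived".
- **3.2.1**: "Patients must be older than 3 years and less than or equal to 25 years of age at the time of enrollment". Section 9.9 makes both sexes eligible.
- **Pregnancy testing.** The note under the therapy delivery map in 4.3 reads: "Obtain prior to starting cycle one only for females of childbearing potential". Footnote 2 of the 7.1 schedule reads: "Required for all females of childbearing potential as a baseline study, then continue to follow institutional guidelines regarding pregnancy testing". The text of 7.1 adds: "At Aflac, monthly pregnancy test for females of childbearing potential".
- **8.1** lists pregnancy on study among the reasons for stopping protocol therapy.
- **3.4.1** makes consent a condition of entry: "a signed informed consent document will be obtained prior to entry onto the study".
- **Appendix 3**, item 13, asks whether the patient is pregnant or breast-feeding. The checklist has no contraception item for either sex.

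**The concern.** The reason given in 3.3.5 for excluding pregnancy at entry does not lapse once treatment starts. Treatment can run for 26 cycles of four weekly doses, which is 104 weeks. The sponsor judged contraception important enough to make it an entry condition in relation to male patients. Yet the patients who would themselves carry a pregnancy while taking the drug have no matching criterion, and the plan gives no reason for the difference.

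Because the criteria are to be read literally, an investigator is not invited to supply an unwritten one. What is at stake is fetal exposure to a drug whose fetal effects the plan calls unknown. This is a matter of patient safety, not of inference.

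**Working it through.** The check is mainly a reading of the text, followed by a small illustration of exposure. The plan gives no figure of its own to reproduce.

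**Step 1: search the criteria.** Inclusion criteria 3.2.1 to 3.2.11 do not mention contraception. Among exclusions 3.3.1 to 3.3.13 it appears once, in 3.3.11. The unwillingness in 3.3.11 could be the patient's or his partner's; on either reading the criterion concerns male patients. Section 3.4 adds nothing on contraception.

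**Step 2: can a female of childbearing potential enroll?** Yes. The age limit in 3.2.1 is 25 years. Sections 9.12 and 9.13 speak of patients under 21, while checklist item 1 repeats 25. Either limit includes such patients, and the testing rules in 4.3 and 7.1 expect them.

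**Step 3: do the other provisions fill the gap?**

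| Provision | Where | What it does |
|---|---|---|
| Pregnancy or breast-feeding exclusion | 3.3.5 | Screens out a current pregnancy |
| Baseline test | 4.3 map, 7.1 footnote 2 | Detects a pregnancy at entry |
| Monthly test at the centre | 7.1 text | Detects a pregnancy on treatment |
| Removal from therapy | 8.1 | Acts once a pregnancy is known |
| Post-therapy evaluation | 7.1 | Lists no pregnancy test |

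None of these prevents a pregnancy. After treatment, 3.3.11 sets 8 weeks in relation to males; no period is stated for females.

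**Step 4: illustrative exposure between tests.** Inputs: weekly dosing at 1 mcg/kg (4.1, 4.3) and monthly testing (7.1). The plan does not define monthly in days, so I take 28 and 31 days as the range. Suppose a pregnancy begins just after a negative test on day 0, with a dose that day.

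- Next test on day 28: doses on days 0, 7, 14 and 21, so 4 doses.
- Next test on day 31: doses on days 0, 7, 14, 21 and 28, so 5 doses.
- Nominal exposure: 4 × 1 = 4 mcg/kg to 5 × 1 = 5 mcg/kg.
- If that test misses the pregnancy and the following one finds it: 8 doses by day 56 (last on day 49), or 9 by day 62 (last on day 56).
- Rounding up to the next 5 mcg (4.1, 4.3) raises the exposure. A 41 kg patient would receive 45 mcg, and 45/41 = 1.10 mcg/kg per dose, so 4 to 5 doses give about 4.4 to 5.5 mcg/kg.

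The 5-day dosing window is ignored. These figures show scale only; they do not estimate how often exposure would occur.

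**The case against.** The strongest reply is that the safeguard may sit in the consent form. Signed consent is required before entry, and the form was not part of the text available for this review. A reader might infer from section 3 that the trial asks no contraception of female patients at all. The documents do not support that, because absence from the eligibility criteria is not absence from the trial. This part of the objection stands and limits the claim. If the consent form does contain such wording, the change brings section 3 into line with it.

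A second reply is that pregnancy risk is already managed, through exclusion, testing, removal, and the general duty in 3.4.2 to meet institutional, FDA and NCI requirements. It would indeed be wrong to infer that the plan ignores the risk. These provisions narrow the gap, but they detect or react, and 3.4.2 names no contraception requirement. Nor does 3.3.9, on patients unwilling or unable to comply, since the criteria contain no female contraception rule to comply with.

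Third, few patients may be affected. Planned enrollment is 20 of both sexes (9.1), and 2.1 says these tumors occur mostly in young children. That stands too, and it keeps the point minor.

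Finally, a bare extension of 3.3.11, applied literally, could shut out a post-menarchal girl who is not sexually active and declines contraception. This is a fair criticism of a careless fix, and the wording below allows for it.

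**Conclusion.** The point holds, limited to the eligibility text. Read literally, the criteria admit a female patient of childbearing potential who is not using contraception, while contraception is an entry condition in relation to male patients.

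The illustrative exposure before detection is about 4 to 5 weekly doses. This assumes that monthly means 28 to 31 days and that the next test detects the pregnancy; it is more if that test does not. The number of patients concerned is unknown, cannot exceed the 20 planned enrollments, and may be small.

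No statistical figure in the plan changes. A reader should not infer any effect on the two-stage design, the response analysis or the toxicity rule. This is a cheap improvement: minor, and about patient safety only.

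**What to change.** Extend 3.3.11 to exclude female patients of childbearing potential who are not willing to use adequate contraception during the study and for a stated period after the last dose. Say in the same criterion that abstinence counts as adequate for those who are not sexually active. The post-treatment period could be the 8 weeks already used in relation to males, or another that the sponsor sets and justifies.

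Add one contraception item covering both sexes to the Appendix 3 checklist, so that the existing male criterion is also checked at enrollment. Confirm that the consent form says the same.

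The cost is about one sentence and one checklist line, submitted as an amendment. The downside is that a few unwilling patients would not be enrolled, in a trial that expects about one patient every 2.1 months (9.1). The abstinence provision should keep that number low.

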3.4 Regulatory

3.4.1

All patients and/or their parents or legal guardians must sign a written informed consent.

The investigational nature and research objectives of this trial, the procedures and treatments involved and their attendant risks and discomforts and benefits, and potential alternative therapies will be carefully explained to the patient, the patient's parents or guardian if he/she is a child, or previously assigned DPA and a signed informed consent document will be obtained prior to entry onto the study.

The PI or an associate investigator on the trial will obtain consent. Where deemed appropriate by the clinician and the child's parents or guardian, the child will also be included in all discussions about the trial and verbal assent will be obtained. The parent or guardian will sign the designated line on the informed consent attesting to the fact that the child has given assent.

3.4.2

All institutional, FDA, and NCI requirements for human studies must be met.

4.0 TREATMENT PROGRAM

Timing of protocol therapy administration, response assessment studies, and surgical interventions are based on schedules derived from the experimental design or on established standards of care. Minor unavoidable departures (+/- up to 5 days) from protocol directed therapy (and up to 1 week for surgery) and/or disease evaluations for valid clinical, patient and family logistical, or facility, procedure and/or anesthesia scheduling issues are acceptable. If an unavoidable departure occurs, patients should continue to follow the roadmap and diary and get assessments within the 5 day period, with the exception of course 1.

4.1 Overview of the treatment plan

Treatment with pegylated interferon alpha-2b must begin within 14 days of patient enrollment. Patients may be pre-medicated as needed with acetaminophen 10-15 mg/kg (maximum 650 mg per dose) or ibuprofen 10 mg/kg within 1 hour of receiving Pegylated interferon. The patients can continue on either acetaminophen or ibuprofen for up to 48 hours after Pegylated interferon injection. The maximum dose of ibuprofen in a 24-hour period will be 40 mg/kg. Ibuprofen for Adolescents and Adults the maximum daily dose: 2.4 grams in 24 hours. Premedication is optional.

Each cycle of therapy will consist of pegylated interferon alfa-2b administered subcutaneously once weekly (**+/- 5days**) for 4 weeks for up to 2 years. Each dose should be administered on the same day

each week. There will be no breaks between cycles. Total number of cycles 26. Each dose is 1µg/kg subcutaneously. Nursing staff will instruct the patients or their caregivers regarding sites of injection and injection technique. Teaching needs to be documented. Rotating the sites of injection is strongly recommended.

Patients and/or their caregivers will be asked to maintain a diary (Appendix 5) documenting the dose of pegylated interferon alpha-2b given, site of administration and any side effects. This diary will be reviewed at each clinic visit. Patients will return to the Aflac clinic prior to start next cycles.

Doses could be rounded up to the nearest upper 5mcg for easier administration. For patients whose weight is greater than 150kg the maximum dose of Pegylated interferon to be administered is 150mcg/dose/ week.

MRI brain and /or spine will be performed as a baseline within **30 days** of enrollment and subsequently every 3 cycles.

See section 7.1 for required observations prior to start therapy.

